7.1.3. Immunogenicity

- For a given subject and the analysis of a given immunogenicity measurement, missing or un-evaluable measurements will not be replaced.
- A seronegative subject is defined as a subject whose antibody concentration is below the assay cut-off value.
- A seropositive subject is defined as a subject whose antibody concentration is greater than or equal to the assay cut-off value.
- Antibody concentrations below the assay cut-off will be given an arbitrary value of half the assay cut-off for the purpose of geometric mean concentration (GMC) calculation.
- Calculation of the GMCs will be performed by taking the anti-logarithm in base 10 (anti-log10) of the mean of the log10 concentration transformations.

Statistical Analysis Plan

Study alias & e-track number(s): NTHi-004 (200157)

- The assay cut-off is the value under which there is no quantifiable result for which no accuracy and precision can be reported. For an assay with a specific 'cut_off' , numerical immuno result is derived from a character field (rawres):
 - If rawres is 'NEG' or '-' or '(-)', numeric result= cutt_off/2,
 - if rawres is 'POS' or '+' or '(+)', numeric result = cut_off,
 - if rawres is '< value' and value<=cut_off, numeric result =cut_off/2,
 - if rawres is '< value' and value>cut_off, numeric result =value,
 - if rawres is '> value' and value<cut_off, numeric result =cut_off/2,
 - if rawres is '> value' and value>=cut_off, numeric result =value,
 - if rawres is '<= value' or '>= value' and value<cut_off, numeric result =cut_off/2,
 - if rawres is '<= value' or '>= value' and value>=cut_off, numeric result =value,
 - if rawres is a value < cut_off, numeric result = cut_off/2,
 - if rawres is a value >= cut_off, numeric result = rawres,
 - else numeric result is left blank.
- All CI computed will be two-sided 95% CI.

Impact of the investigational vaccine on AECOPD

- For a given subject and the analysis of a given laboratory assay, missing or un-evaluatable measurements will not be replaced.
- Subjects who did not have any sputum collected during at least 1 AECOPD (if at least 1 AECOPD occurred) will not be taken into account for the NTHI-associated AECOPD analyses.
- For summaries of the number of AECOPD occurring during the 1 year follow-up period starting 1 month post-Dose 2, an exacerbation rate will be calculated for each subject. The number of exacerbations during the 1-year follow-up period will be imputed for subjects withdrawing from the study to provide an estimate of the number of exacerbations over the follow-up period. This calculation will only be performed for purposes of reporting summary statistics for the rate of exacerbations during the 1 year follow-up period since the modelling of exacerbations takes into account the number of exacerbations and the time of follow-up for each subject. The calculation of exacerbation rate will be based on follow-up period intervals to avoid obtaining high imputed rates if a subject withdrew very early in the follow-up period after experiencing an exacerbation. Since treatment courses for moderate/severe exacerbations are $\leq 2 - 4$ weeks when appropriate, calculated numbers of exacerbations for subjects withdrawing from the study will be based on 4-week intervals of the follow-up period. For subjects followed for less than 1 year, the number of exacerbations during the 1-year follow-up period will be calculated by multiplying the number of exacerbations experienced by the subject by 13 and dividing by the number of 4-week periods the subject was followed up:

Statistical Analysis Plan

Study alias & e-track number(s): NTHi-004 (200157)

Number of exacerbations per year = Number of exacerbations * 13 /Number of 4-week treatment period intervals

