7.5. Contraindications to subsequent vaccination

The following events constitute contraindications to administration of the investigational NTHi vaccine at that point in time; if any of these events occur at the time scheduled for vaccination, the subject may be vaccinated at a later date, within the time window specified in the protocol, or the subject may be withdrawn at the discretion of the investigator (see Section 9.5).

- Moderate or severe AECOPD that is on-going or that has not been resolved for at least 7 days at the time of vaccination.
- Acute disease and/ or fever at the time of vaccination.
 - Fever is defined as oral or axillary temperature $\geq 37.5^{\circ}\text{C}$. The preferred route for recording temperature in this study will be oral.
 - Subjects with a minor illness without fever can be administered all vaccines at the discretion of the investigator.

The following events constitute absolute contraindications to further administration of the investigational NTHi vaccine. If any of these events occur during the study, the subject must not receive vaccine Dose 2.

- Anaphylaxis following the administration of vaccine.
- Pregnancy.

- Any confirmed or suspected immunosuppressive or immunodeficient condition, based on medical history and physical examination (no laboratory testing required).
- Current immune-mediated disease other than COPD.
- Malignancy (excluding non-melanotic skin cancer and carcinoma *in situ* of the cervix, if considered cured) or lymphoproliferative disorder.
- Any other event which the investigator judges may put the safety of the subject at risk through vaccination.

For subjects meeting one of the above specified contraindications to subsequent vaccination before administration of vaccine Dose 2, the study visit at Day 67 (Visit 5) will be cancelled. These subjects will be invited to all other study visits as planned (including AECOPD-driven study visit[s] and/ or phone contact[s]) and will continue all study procedures as planned, with the exception of blood sampling for immunogenicity (humoral and CMI) and biomarkers and sputum sampling.

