11.6. Derived and transformed data

The study groups will be defined by treatment actually administered at Dose 1.

Demography

- For a given subject and a given demographic variable, missing measurement will not be replaced.

Safety

- For solicited symptoms, the analysis will exclude subjects with missing or un-evaluable measurements (*i.e.* total analysis of solicited symptoms will include all vaccinated subjects with documented solicited symptom sheets).
- For the unsolicited symptoms and concomitant medications/ products/ vaccinations, subjects who miss reporting symptoms/concomitant medications/ products/ vaccinations will be treated as subjects without unsolicited symptoms or concomitant medications/ products/ vaccinations, respectively.

Immunogenicity

- For a given subject and the analysis of a given immunogenicity measurement, missing or un-evaluable measurements will not be replaced.
- A seronegative subject is defined as a subject whose antibody concentration is below the assay cut-off value.
- A seropositive subject is defined as a subject whose antibody concentration is greater than or equal to the assay cut-off value.
- Antibody concentrations below the assay cut-off will be given an arbitrary value of half the assay cut-off for the purpose of geometric mean concentration (GMC) calculation.

- Calculation of the GMCs will be performed by taking the anti-logarithm in base 10 (anti-log10) of the mean of the log10 concentration transformations.

Impact of the investigational vaccine on AECOPD

- For a given subject and the analysis of a given laboratory assay, missing or un-evaluable measurements will not be replaced.
- Subjects who did not have any sputum collected during at least 1 AECOPD (if at least 1 AECOPD occurred) will not be taken into account for the NTHI-associated AECOPD analyses.

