6.1.3. Analysis of impact of the investigational vaccine on AECOPD incidence

The analysis will be performed on the ATP cohort for efficacy. If the percentage of vaccinated subjects excluded from the ATP cohort for efficacy is more than 10%, a second analysis based on the TVC will be performed to complement the first analysis.

The following incidence rates will be computed over a period starting 1 month post-Dose 2 and lasting for 1 year, with 95%CI:

- NTHi-associated moderate and severe AECOPD. (See definition in section 7.1.4)
- NTHi-associated all-severity AECOPD.
- All-cause moderate and severe AECOPD.
- All-cause, all-severity AECOPD.

Vaccine efficacy (VE) for AECOPD events will be defined as:

$$VE (AECOPD) = 1 - R_{vaccine} / R_{control}$$

with:

- $R_{vaccine}$ = average yearly incidence rate of AECOPD events per subject in the group 10-AS01E.
- $R_{control}$ = average yearly incidence rate of AECOPD events per subject in the Control group.

In case the 95% CI of the VE cannot be estimated, *e.g.* when no event is observed in the group 10-AS01E (leading to a VE of 100%), then an exact procedure will be used to estimate a VE and its 95% CI. This exact procedure will be based on the number of subjects with event instead of on the average number of event per subject in each group.

Statistical Analysis Plan

Study alias & e-track number(s): NTHi-004 (200157)

VE in the prevention of NTHi-associated moderate and severe AECOPD and its 95% CI will be calculated.

VE in the prevention of NTHi-associated all-severity AECOPD, of all-cause moderate and severe AECOPD and of all-cause, all-severity AECOPD and their 95% CI will also be calculated.

The 95%CI of the incidence rate will be computed using a model which accounts for repeated events. The Generalised linear model assuming the Negative Binomial distribution for the response variable with logarithm as link function, and the logarithm of time for follow-up as an offset variable will be used. In addition, the following covariates (as per randomization) will be taken into account:

- country,
- number of moderate/severe exacerbations reported in the 12 months prior to enrolment,
- COPD status at enrolment (derived by GSK from the Visit 1 spirometry results)
- Age (below or equal to median/above median)

If the model does not converge, the Poisson distribution will be used instead of the Negative Binomial one.

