7.1.4. NTHi associated AECOPD

An NTHi associated to AECOPD is not yet well defined at the time of the SAP is written. Here is the first approach:

- An AECOPD for which NTHi was observed: Hi confirmed first by culture and then by PCR.

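### The rule for AECOPD without sputum has two readings; under either, NTHi-associated incidence is underestimated if sampling is unrelated to NTHi status, and VE is biased if sampling differs by group

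*SAP*

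**What the plan says.** Protocol 11.6 and SAP 7.1.3 (under the sub-heading on vaccine impact on AECOPD) carry the same exclusion: "Subjects who did not have any sputum collected during at least 1 AECOPD (if at least 1 AECOPD occurred) will not be taken into account". The clause in brackets protects subjects who never exacerbate; they remain with zero events.

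The surrounding rules fix what happens to the rest:

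- On missing results, SAP 7.1.3 states: "For a given subject and the analysis of a given laboratory assay, missing or un-evaluatable measurements will not be replaced".
- The provisional case definition in SAP 7.1.4 is: "An AECOPD for which NTHi was observed: Hi confirmed first by culture and then by PCR". Without a sample, an episode cannot meet it.
- SAP 6.1.3 fits a negative binomial model in which "the logarithm of time for follow-up as an offset variable will be used", over the year that begins one month after Dose 2. VE is one minus the ratio of the yearly rates in the two groups.

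Sputum at an AECOPD visit is taken only if the investigator judges it safe (Protocol Table 8, footnote d). Under SAP 7.1.11.2, some e-diary alerts without a site visit can still qualify as AECOPD although no laboratory data exist. SAP 6.1.7.1 tabulates how many subjects provide sputum, but nothing links that table to the incidence or VE analysis. No sensitivity analysis for unsampled AECOPD is specified.

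**The concern.** Membership of the analysis set depends on the outcome, since only a subject with an event can be excluded. Follow-up from event-free subjects stays in the denominator, while some NTHi events are lost from the numerator, either with an excluded subject or as an unsampled episode in a retained one.

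The sentence also has two meanings. On the narrow reading, a subject is dropped only if none of their AECOPD was sampled. On the broad reading, one unsampled AECOPD is enough, which preferentially removes frequent exacerbators. Nor does the rule say whether an AECOPD before the one-year window counts. Two programmers could follow the text faithfully and report different rates.

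At stake are the incidence and VE for NTHi-associated moderate and severe AECOPD. This is the first-listed tertiary endpoint and matches the indication in the synopsis. The all-cause AECOPD analyses are untouched.

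**Working it through.** **The plan's own figures.** None is given for the NTHi analyses. The only sample-size figures (Protocol 11.4) concern detecting an adverse event with 70 subjects. They reproduce: 1 − 0.99^70 = 50.5% and 1 − 0.95^70 = 97.2%.

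**Inputs.** From the documents: about 70 subjects per group, 1:1 allocation, one year of follow-up, and an NTHi share of AECOPD of 11–38% (Protocol 1.1.1). Assumed, because the documents do not give them: all-cause rate L = 1 per year (range 0.5–2), negative binomial dispersion k = 0.5 (range 0–1), and probability s that an AECOPD is sampled, at first unrelated to NTHi status.

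**Formulas.** P(no event) at mean m is (1 + km)^(−1/k).

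- Narrow: the fraction dropped is D = P(no sampled AECOPD) − P(no AECOPD), and observed/true incidence = s/(1 − D). Dropped subjects have no observable NTHi event, so only the denominator shrinks.
- Broad: observed/true = s/(1 + kL(1 − s)), and the fraction dropped is 1 − (1 + kL(1 − s))^(−1/k).
- Keep everyone and count unsampled AECOPD as negative: observed/true = s.

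**Example, s = 0.80.** Narrow: D = 1.4^(−2) − 1.5^(−2) = 0.510 − 0.444 = 0.066, and 0.80/0.934 = 0.856. Broad: 0.80/1.10 = 0.727, with 1 − 1.1^(−2) = 17.4% of subjects dropped. A simulation of 1,000,000 subjects gave 0.856 and 0.726.

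| Unsampled | Narrow | Broad | Keep all, count as negative |
|---|---|---|---|
| 10% | 0.93 | 0.86 | 0.90 |
| 20% | 0.86 | 0.73 | 0.80 |
| 30% | 0.78 | 0.61 | 0.70 |

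Across the assumed ranges of L and k, at 20% unsampled, the narrow factor lies between 0.84 and 0.87 and the broad factor between 0.57 and 0.80.

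**Sampling related to NTHi status** (simulation, NTHi share 25%):

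- 100% of positive and 70% of negative episodes sampled: narrow 1.08, broad 0.90.
- 95% and 75%: narrow 1.02, broad 0.87.
- 60% and 85%: narrow 0.64, broad 0.54.

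**VE, equal sampling (s = 0.80 in both groups).** With true VE 30%, apparent VE is 30% (narrow) and 29–30% (broad). If the vaccine halved the all-cause rate (true VE 50%), apparent VE is 50–51% (narrow) and 45–50% (broad) over k = 0 to 1.

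**VE, unequal sampling (L = 1, k = 0.5).**

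- True VE 0, 70% sampled in vaccine and 90% in control: narrow 1 − 0.781/0.929 = +16%; broad 1 − 0.609/0.857 = +29%. Reversed: −19% and −41%.
- True VE 30%, same gap: 41% and 50%. Reversed: 17% and 1%.
- True VE 30%, a ten-point gap (80% and 90%): about 36% and 40%. Reversed: 24% and 17%.

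**The case against.** **The exclusion is not always the culprit.** A reader might infer that dropping these subjects is what pushes incidence down. Under the narrow reading this is wrong. The deficit comes from unsampled episodes, and removing the person-time of subjects with no observable result moves the estimate back towards the truth (0.86 against 0.80). This stands. Only under the broad reading, with overdispersion, does the exclusion itself add to the loss.

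**Downward is not certain.** It rests on sampling being unrelated to NTHi status, or lower in positive episodes. If mainly NTHi-negative episodes go unsampled, the narrow reading can overstate incidence, by 2–8% in the cases above. This stands too, although the documented reasons for missing sputum do not point that way.

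**A VE bias should not be inferred from the rule alone.** Allocation is randomised, clinical evaluators are blinded (Protocol 6.3), subjects must be regular sputum producers (5.2) and induced sputum is allowed (6.6.15.2). The documents show no sampling gap between groups. One could arise if vaccination changed AECOPD severity and hence who can safely be sampled, but that is a possibility, not a finding.

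**Protocol 7.5 supports less than it seems to.** Subjects with a contraindication to Dose 2 continue study procedures "with the exception of blood sampling for immunogenicity (humoral and CMI) and biomarkers and sputum sampling". A reader might take this as guaranteed missing sputum in the main analysis. But that analysis uses the ATP efficacy cohort, which requires compliance with the vaccination schedule. These subjects matter mainly in the complementary TVC analysis, run only if more than 10% are excluded.

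**Precision.** With 70 per group, an assumed 30% NTHi share and true VE 30%, expected NTHi events are 21 against 14.7 at 1 AECOPD per year, or 42 against 29.4 at 2. Poisson 95% intervals for VE then run from about −36% to 64%, or −12% to 56%. A shift of a few points is small beside these. That lowers the priority; it does not make the rule clear or the incidence estimate unbiased.

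**Conclusion.** The concern holds in limited form. Followed as written, the plan underestimates NTHi-associated incidence when sampling is unrelated to NTHi status: by about 7%, 14% and 22% (narrow) or 14%, 27% and 39% (broad) at 10%, 20% and 30% unsampled, given the assumed 1 AECOPD per year and dispersion 0.5. The two readings differ enough that the sentence needs settling in any case.

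VE is nearly unaffected when sampling is equal between groups and biased in either direction when it is not. The actual sampled fractions are unknown from the documents.

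The endpoint is tertiary, and Protocol 11.13 calls group comparisons descriptive and to be read with caution. The change is therefore one that should be made, without threatening the study's primary conclusions.

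**What to change.** Amend SAP 7.1.3, and Protocol 11.6 to match:

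1. Keep every subject in the cohort and all their person-time in the NTHi-associated analyses.
2. Treat the NTHi status of an unsampled AECOPD as missing. Correct for it with a simple model: weight sampled AECOPD by the inverse of the sampled fraction within group and severity, or impute status by group and severity. State the missing-at-random assumption. With a few dozen events, a richer model would be fragile.
3. Add best- and worst-case bounds, with unsampled AECOPD taken as all negative or all positive, including opposite assignments in the two groups for VE.
4. Report the fraction of AECOPD sampled, by group, beside the incidence and VE.
5. Keep the present exclusion as a sensitivity analysis, reworded to one reading and restricted to AECOPD in the one-year window.

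Step 1 must not be adopted without step 2: keeping everyone and counting unsampled AECOPD as negative gives 0.80 at 20% unsampled, against 0.86 under the narrow reading. With status missing at random and the model correct, the expected factor is 1.00.

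The cost is one SAP paragraph, modest programming and an explicit assumption that the data cannot verify. No additional data collection is needed.

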7.1.4. NTHi associated AECOPD

An NTHi associated to AECOPD is not yet well defined at the time of the SAP is written. Here is the first approach:

- An AECOPD for which NTHi was observed: Hi confirmed first by culture and then by PCR.

7.1.5. HRQOL

The CAT index will be derived as the sum of the ratings recorded for each of the eight individual items. Each of these items has 6 possible scores (0, 1, 2, 3, 4 or 5), leading to a range of 0 to 40 for CAT score.

7.1.6. EXACT-PRO derived AECOPD definitions and calculation rules

Start of an EXACT-PRO signal for exacerbation (as in EXACT-PRO user Manual and in Makay, et al., 2014):

1. *An EXACT-PRO exacerbation is defined as a 12 point increase above baseline for 2 consecutive days, or a nine point increase for 3 consecutive days.*
2. *The baseline score corresponds to the average EXACT score during a baseline period defined as days 14 to 8 preceding exacerbation onset*
3. *Exacerbation onset will be taken as the first day in which at least two symptoms (at least 1 major) are present and have not been discounted (see above).*
4. *Only symptom data collected during the study period will be used to define the start of an exacerbation.*

End/recovering of an EXACT-PRO signal of an exacerbation:

1. *The end/recovering of an EXACT-PRO signal of an exacerbation corresponds to the day at the EXACT-PRO score return to its baseline value.*
2. *The length of a signal of an exacerbation will be at least of 2 days. So rule 1 will only apply from the third day onwards.*

Missing data:

Days with missing data will not be ignored when defining start of a signal: e.g., if a patient has two qualifying symptoms followed by a missing day, if the next day with data has two qualifying symptoms this will not be defined as an exacerbation.

Statistical Analysis Plan

Study alias & e-track number(s): NTHi-004 (200157)

7.1.7. “e-diary derived AECOPD” definitions and calculation rules

The definition of an AECOPD case definition from section 5.3.1.2 of the Protocol is what we will call here an “e-diary derived (AECOPD) signal”. In this paragraph, only the derivation of occurrence and length of e-diary signals is described. Derivation of occurrence and length of AECOPDs is described in Section 7.1.11.

Start of an e-diary signal for exacerbation:

1. An exacerbation is defined as a worsening of at least 2 symptoms for ≥ 2 consecutive days where at least one of the symptoms is major.
2. The same two symptoms do not have to be present on both days as long as at least one major symptom is present on both days.
3. Any symptom that has occurred consecutively for 5 days or more prior to a potential exacerbation should be discounted from the symptoms that define an exacerbation.
4. Exacerbation onset will be taken as the first day in which at least two symptoms (at least 1 major) are present and have not been discounted (see above).
5. Only symptom data collected during the study period will be used to define the start of an exacerbation.

7.1.8. End/Duration of an e-diary signal of an exacerbation:

1. The end/recovering of an e-diary signal of an exacerbation corresponds to the day at which the 3-day moving average of the daily symptom count score (average between the day the day before and the day after) to return to baseline symptom count score (the mean daily symptom count score over days 14 to 8 preceding exacerbation onset). For a specific day, the daily symptom count score is defined as the sum of the symptom scores experienced in this day (a major symptom accounts for 2 points, a minor symptom accounts for 1 point, as in Trappenburg *et al.*, 2011, but contrary to Seemungal *et al.* 2000 and Mackay *et al.* 2014, in which all symptoms accounted to 1). Note that the symptoms that have occurred consecutively for 5 days or more prior to a potential exacerbation and that are discarded for these exacerbations are not discarded from the symptoms counts.
2. The length of an e-diary signal of an exacerbation will be at least of 2 days. So rule 1 will only apply from the third day onwards.
3. The baseline symptom count score is calculated as the average count score of the observed days in the period used to calculate the baseline symptom count score. For example, if an exacerbation occurs from day 10 onwards, the

Statistical Analysis Plan

Study alias & e-track number(s): NTHi-004 (200157)

baseline period will be the average between day1 and day2 (day10 - 8 days= day2, day10 - 9 days = day1, Day1 being the first study day). For exacerbations before day 9 but after day 2, the baseline symptom score will be considered to be day1

4. If the first e-diary signal of an exacerbation is occurring before day 3: duration will be counted until the day in which there is at most 2 majors or 1 major and one minor symptom.
5. Recovery time is calculated as the number of days from exacerbation e-diary signal onset (included) to exacerbation e-diary signal end (not included).

7.1.9. Time between 2 e-diary signals for exacerbations/evaluation of baseline symptom score:

The minimum duration between 2 e-diary signals with distinct baseline value is 15 days, which is the minimal period for which a new full exacerbation-free baseline can be calculated for the next e-diary episode.

If a new worsening of symptoms occurs between 6 and 14 days of a previous exacerbation, the baseline period used will be the same baseline as the one of the original exacerbation. Therefore, it will last until the daily symptom count score has gone below the baseline symptom score of the previous event.

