4. AECOPD

4.1. Detection of AECOPD

Occurrence of each potential **AECOPD** will be monitored by means of electronic Diary Cards which the subject will use to record his/ her morning symptoms on a daily basis. The electronic Diary Cards will be programmed as to detect each potential AECOPD as follows (based on the Anthonisen criteria [Anthonisen, 1987]):

- Worsening of two or more of the following major symptoms for at least two consecutive days: dyspnoea, sputum volume, sputum purulence (colour), OR
- Worsening of any one major symptom together with any one of the following minor symptoms for at least two consecutive days: sore throat, colds (nasal discharge and/ or nasal congestion), fever (oral temperature $\geq 37.5^{\circ}\text{C}$) without other cause, increased cough, increased wheeze.

Note that:

- The same two symptoms do not have to be present on both days as long as at least one major symptom is present on both days.
- Any symptom occurring on at least 5 consecutive days prior to a potential exacerbation will be discounted from the symptoms that define an exacerbation.

Each time a potential AECOPD is detected via the electronic Diary Card, the device will alert the subject to contact the study site, and at the same time an alert will be sent to the site so that the site staff contacts the subject to check whether an AECOPD visit is warranted. In addition, the site should pro-actively follow-up all data received via the electronic Diary Card and contact the subject whenever deemed necessary.

During the contact with the subject, the site will determine whether the subject might actually be experiencing an AECOPD (e.g. notifications that can be explained solely by increased physical activity will not be considered).

For all potential AECOPD detected between first vaccination and study conclusion:

- If the site concludes that the subject is not experiencing an AECOPD, this should be documented/ reported.
- If the site concludes that the subject may be experiencing an AECOPD, an AECOPD visit will be scheduled as soon as possible after the onset of AECOPD symptoms as recorded in the electronic Diary Card or confirmed by the subject (maximum 96 hours after and, if applicable, preferably before starting treatment with antibiotics) *.

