6.1.4. AECOPD visits and daily questionnaires

The time until first AECOPD as of 1 month post-Dose 2 will be computed with exact 95% CI by group. Subjects who exacerbate before 1 month post-Dose 2 will not be taken into account in this analysis.

The number of morning e-dairy (PHT) alerts (resp. evening e-diary alerts (EXACT-PRO)) with and without corresponding site visits will be tabulated. The reason for inconsistency between morning e-diaries and site visits will also be presented.

The number of exacerbation site visits with confirmed AECOPD with and without morning e-diary alerts (resp. evening e-diary alerts (EXACT-PRO)) will be tabulated along with the reason for no e-diary alert.

Concordance/discordance of exacerbations periods as defined clinically or via the morning diary cards or the evening diary cards will be tabulated and presented graphically.

The percentage of spontaneous exacerbation visits will be tabulated as well as the percentage of monthly visits with recovered/stable status.

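### SAP 7.1.6 defines an EXACT-PRO event by a score rise but dates its onset, and so anchors its baseline and end, with the morning e-diary symptom rule

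*SAP*

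**What the plan says.** Section 7.1.6 of SAP Amendment 1 sets out the EXACT-PRO derivation.

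- Item 1 defines the event by score: "a 12 point increase above baseline for 2 consecutive days, or a nine point increase for 3 consecutive days".
- Item 2 anchors the baseline on onset: "The baseline score corresponds to the average EXACT score during a baseline period defined as days 14 to 8 preceding exacerbation onset".
- Item 3 gives the onset day: "Exacerbation onset will be taken as the first day in which at least two symptoms (at least 1 major) are present". It adds that the symptoms must not have been discounted, and refers the reader to text above.
- Item 4 limits the data used to symptom data from the study period.
- The event ends when the EXACT-PRO score returns to the baseline value.
- The missing-data example is worded in qualifying symptoms. It does not mention a score.

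The only discounting rule is in 7.1.7 item 3, which comes after 7.1.6: "Any symptom that has occurred consecutively for 5 days or more prior to a potential exacerbation should be discounted". Protocol 4.1 lists the major symptoms ("Worsening of two or more of the following major symptoms for at least two consecutive days") for a diary in which the subject is to "record his/ her morning symptoms on a daily basis". Protocol section 3 lists the EXACT-PRO as a separate bedtime entry.

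SAP 6.1.4 then uses the derived periods: "Concordance/discordance of exacerbations periods as defined clinically or via the morning diary cards or the evening diary cards will be tabulated". It also tabulates evening EXACT-PRO alerts with and without a site visit, and confirmed visits with and without an evening alert.

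**The concern.** An event defined on one instrument should be dated on that instrument. Here a bedtime score decides whether an event exists, while a rule written for morning symptoms decides when it starts. Because the baseline window hangs on the start day, and the rise and the end are both measured against that baseline, the borrowed date reaches the whole derivation.

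What is at stake is the instrument comparison in 6.1.4. If the evening period takes its start from the morning diary, the two share information that the comparison treats as separate. Score rises with no qualifying symptom day, which are the clearest cases of disagreement, cannot be dated at all. A programmer would have to follow a rule that fails for those events or improvise one that the SAP does not state.

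**Working it through.** The plan gives no figure to reproduce on this point. The check is a comparison of text, followed by an illustration on assumed score paths.

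**1. The two derivations side by side**

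| Element | EXACT-PRO, 7.1.6 | Morning e-diary |
|---|---|---|
| Event | Score rise (item 1) | At least two symptoms, one major, on 2 or more consecutive days (7.1.7 item 1) |
| Discounting rule | None | 7.1.7 item 3 |
| Onset | Item 3 | 7.1.7 item 4, same sentence |
| Data used | Item 4 | 7.1.7 item 5, same sentence |
| Missing-data example | Symptoms | 7.1.10 item 1, same example |
| Baseline if onset is early in the study | None | 7.1.8 item 3 |

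The reference to text above in 7.1.6 item 3 has nothing to point to within 7.1.6. In 7.1.7 the same reference does have a target. The text appears to have been carried over from the morning-diary rules. SAP version 1 reads the same way, so Amendment 1 did not correct it.

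**2. The chain of dependence**

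Symptom day → onset (item 3) → baseline (item 2) → rise above baseline (item 1) and return to baseline (end rule). With no symptom day the chain has no starting point. The SAP gives no fallback and no limit on how far the symptom day may lie from the score rise.

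**3. Illustration**

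Let S(d) be the score on day d and o the onset day. The baseline is B(o) = [S(o−14) + … + S(o−8)] / 7, a mean over seven days. Both score paths below are assumptions.

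*Step path:* S = 40 to day 29 and 54 from day 30. The score-based onset is day 30, with B = 40.0 and a rise of 14.

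| Symptom onset relative to day 30 | Baseline | Maximum rise | Item 1 met? |
|---|---|---|---|
| −7 to +7 days | 40.0 | 14.0 | yes |
| +8 | (6×40 + 54)/7 = 42.0 | 12.0 | yes |
| +10 | (4×40 + 3×54)/7 = 46.0 | 8.0 | no |
| +14 | 54.0 | 0.0 | no |

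*Ramp path:* S = 40 to day 23, then 2 points more each day to a ceiling of 54 on day 30. The scores on days 28 to 30 are 50, 52 and 54, all at least 9 above 40, so the score-based onset is day 28 with B = 40.0.

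- Symptom onset 7 days late: B = (3×40 + 42 + 44 + 46 + 48)/7 = 42.9, so the 9-point threshold is 51.9. Day 28 (50) no longer qualifies. The 9-point rule is still met from day 29 (52, 54, 54).
- Symptom onset 10 days late: B = (42 + 44 + 46 + 48 + 50 + 52 + 54)/7 = 48.0. The maximum rise is 6 and item 1 is not met.

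In both paths the recorded onset date moves by the full gap, whatever happens to the baseline.

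**The case against.** The strongest reply is that this is a copying slip with little consequence. Several parts of that stand.

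- Section 7.1.6 never names the morning diary, and the EXACT-PRO items are not in the documents. That the symptoms come from the morning diary is an inference. It rests on the identical sentence, the major/minor labels and the reference with no target. No other source for those terms is given.
- A reader might infer that every EXACT-PRO event gets a wrong onset and baseline. The documents do not support that. Every event passes through the rule, but the date is wrong only when the two days differ, and a small gap after a stable score leaves the baseline unchanged.
- A reader might infer that the rule forces agreement, or removes all EXACT-only events. It does neither. A score rise is still required. Item 3 also needs only one qualifying day, whereas a morning signal needs two consecutive days, so a rise with a single symptom day can be dated and still has no morning signal.
- A reader might infer that the concordance tables exist to refine the AECOPD case definition. Section 6.1.4 states no purpose, and Protocol 1.2.2.1 ties that refinement to information from AECOPD-driven contacts.

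What does not stand is the view that this is only missing detail. The SAP states an onset rule, and that rule does not fit the event it dates.

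**Conclusion.** The point holds as a wrong derivation rule with limited reach. It affects EXACT-derived events and the descriptive alert and concordance tables in 6.1.4. It does not affect AECOPD incidence or vaccine efficacy: under 7.1.11 those events come from clinically confirmed visits, with some reconciled morning signals, and not from EXACT-PRO. Nor does it affect the tertiary EXACT-PRO endpoint, which is the score itself.

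The lean towards agreement has two sources: a shared start day, and the loss of score rises that have no qualifying symptom day. A very late symptom day that cancels an event would act the other way, by leaving a morning signal unmatched.

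The net size cannot be given, because the documents do not say how often or by how much the two days differ. The thresholds of about a week for the baseline and 10 days for loss of the event come from the assumed paths. The verdict also assumes that the major/minor symptoms in 7.1.6 are the morning-diary ones.

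**What to change.** Replace item 3 of 7.1.6 with a score-based scan. For each candidate day, compute the baseline as the mean EXACT score over days 14 to 8 before that day. Onset is the first day from which the score is at least 12 points above that baseline for 2 consecutive days, or at least 9 points above it for 3 consecutive days. The scan has to be written out because onset and baseline each refer to the other. In the illustration it gives onset on day 30 (step) and day 28 (ramp), both with baseline 40.0.

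Three further edits are needed:

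- Restate item 4 and the missing-data rule in terms of EXACT scores.
- State the baseline for events in the first 14 days, when the window is incomplete (the first day with a full window is day 15), as 7.1.8 item 3 does for the morning diary.
- Check the final wording against the EXACT-PRO user manual that the SAP cites. It was not available for this review, so the scan is a proposal consistent with items 1 and 2 and not a statement of what the manual says.

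The cost is a few sentences in 7.1.6 and the matching programming. No new data are needed, and no stated trial figure changes. It should be settled before the 6.1.4 tables are produced.
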